14.6. Secondary Analysis

Change in Overall Quality of Vision from Baseline at 30-Day Follow-Up Using VAS Scores

The overall change of quality of vision from baseline at 30-Day follow-up will be analyzed with the same hypotheses and models as primary analyses. If the Shapiro-Wilks test result is significant, then *Primary Analysis Plan B* will be adapted for overall change of quality of vision at 30-Day follow-up. Otherwise, *Primary Analysis Plan A* will be adapted for this secondary analysis.

Hypothesis Testing:

The two separate null and alternative hypotheses for non-inferiority of Test relative to Control are as follows:

$$H_0: \Delta \le -20 \\ H_A: \Delta > -20$$

where Δ is the difference between treatment group in mean change from baseline at 30-Day follow-up (Test minus Control).

14.7. Other Exploratory Analysis

Exploratory analyses will only be conducted if all primary and secondary hypotheses are met. If conducted, exploratory analysis will be analyzed for the Safety population. The exploratory analyses will be analyzed as follows:

Change in Overall Ocular Comfort from Baseline at 14-Day Follow-Up Using VAS Scores The overall change in ocular comfort from baseline at 14-Day follow-up will be analyzed as described in primary analyses (section 14.5).

Change in Overall Quality of Vision from Baseline at 14-Day Follow-Up Using VAS Scores The overall change in ocular comfort from baseline at 14-Day follow-up will be analyzed as described in secondary analyses (section 14.5).

Corneal Staining (Grade 2 or higher) Using FDA Scale

Corneal staining response using FDA grading scale (i.e. Grade 0 = None, Grade 1 = Trace, Grade 2 = Mild, Grade 3 = Moderate and Grade 4 = Severe) will be monitored by surveillance tabulation by

treatment group. If the rates between groups are significantly different from each other, then further analyses will be performed.

Subject's reported ocular symptoms

Subjects are asked to report if they experienced any ocular symptoms at Baseline and during each follow-up. If the number of reported ocular symptoms exceeds 5% total population, further analyses will be done to investigate the correlation of ocular symptoms to the Test drops.

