2. STUDY OBJECTIVES, ENDPOINTS AND HYPOTHESES

2.1. Objectives

The objective of this study is to evaluate the safety and the efficacy of an Investigational lubricating eye drops (Test) by comparison with Blink[®] Tears eye drops (Control).

This study is being conducted to support product registration in the European Union.

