2.2. Endpoints

Primary Endpoint:

The primary endpoint in this study is change in overall ocular comfort score from baseline at 30-Day follow-up. Subjective overall ocular comfort will be assessed at baseline, 14-Day and 30-Day follow-up using a Visual Analogue Scale (VAS) with continuous scale from 0 (extremely uncomfortable) to 100 (extremely comfortable)⁷.

Secondary endpoint:

The secondary endpoint in this study is change in overall quality of vision score from baseline at 30-Day follow-up. Change in quality of vision from baseline will be assessed using Visual Analogue Scale (VAS) with continuous scale from 0 (extremely uncomfortable) to 100 (extremely comfortable) at 30-Day follow-up⁷.

Other Exploratory Endpoints:

- Corneal Staining
- Subject's reported ocular symptoms
- Tear film break up time
- Slit lamp findings using FDA scale
- End of day ocular comfort
- Snellen best corrected distance visual acuity
- Subjective evaluation of symptom of dryness
- Adverse Events
- Number and reasons for discontinuation will be monitored.
- Change in overall quality of vision from baseline at 14-Day follow-up using VAS
- Change in overall ocular comfort from baseline at 14-Day follow-up using VAS
- PRO and MRD analysis

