- Limbal cell Damage leading to Conjunctivalization

Significant Adverse Events – are defined as events that are symptomatic and warrant discontinuation (temporary or permanent) of the test articles (excluding Serious Adverse Events).

Diagnoses and conditions that are considered Ocular Significant Adverse Events include, but not limited to the following:

- Significant Infiltrative Events (SIE)
- Any Temporary Loss of > 2 Lines of BSCVA
- Other grade 3 or higher corneal findings, such as abrasions or edema
- Corneal events e.g. Epidemic Keratoconjunctivitis (EKC)
- Asymptomatic Corneal Scar
- Any corneal event which necessitates temporary eyedrop discontinuation > 2 weeks

Non-Significant Adverse Events – are defined as those events that are usually asymptomatic and usually do not warrant discontinuation of tear supplement use but may cause further symptoms. However, the Investigator may choose to prescribe treatment as a precautionary measure.

Diagnoses and conditions that are considered Ocular Non-Significant Adverse Events include, but not limited to the following:

• Non-significant Infiltrative Event (NSIE)

- Papillary Conjunctivitis
- Superficial Punctate Keratitis (SPK)
- Conjunctivitis: Bacterial, Viral, Allergic
- Blepharitis
- Meibomianitis
- Contact Dermatitis
- Localized Allergic Reactions or infections
- Any corneal event not explicitly defined as serious or significant adverse event, which necessitates temporary eyedrop discontinuation < 2 weeks

Adverse Drug Reaction (ADR) – An ADR is referred to all "noxious and unintended responses to a drug product related to any dose where a causal relationship between a medical product and an adverse event is at least a reasonable possibility, i.e., the relationship cannot be ruled out."²

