14. STATISTICAL METHODS

14.1. General Considerations

Statistical Analysis will be undertaken by the sponsor or under the authority of the sponsor. A general description of the statistical methods to be implemented in this clinical trial is outlined below.

All data summaries and statistical analyses will be performed using the SAS software Version 9.4 or higher¹⁰. Throughout the analysis of data, the results for each subject/eye will be used when available for summarization and statistical analysis. Unscheduled visits will be summarized separately and will be excluded from any efficacy analyses. However, unscheduled visits will be included in any analysis that may be conducted on safety endpoints.

Summary tables (descriptive statistics and/or frequency tables) will be provided for all baseline variables, efficacy variables and safety variables as appropriate. Continuous variables will be summarized with descriptive statistics (n, mean, standard deviation (SD), median, minimum, and maximum). Frequency count and percentage of subjects or eyes within each category will be provided for categorical data.

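### The only between-arm safety analyses specified in Section 14 (corneal staining, reported symptoms) run only if both efficacy hypotheses are met

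*Combined protocol and SAP*

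**What the plan says.** Section 14.7 (Other Exploratory Analysis) opens with the rule "Exploratory analyses will only be conducted if all primary and secondary hypotheses are met" and then lists four analyses: Day-14 comfort, Day-14 quality of vision, corneal staining of Grade 2 or higher, and subject-reported ocular symptoms. Staining "will be monitored by surveillance tabulation by" treatment group, with further analysis if the rates differ significantly. For symptoms, if reports exceed 5% of the total population, "further analyses will be done to investigate the correlation of ocular symptoms to the Test drops".

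Outside the gate, Section 14.1 says: "Summary tables (descriptive statistics and/or frequency tables) will be provided for all baseline variables, efficacy variables and safety variables as appropriate". The same section adds that "unscheduled visits will be included in any analysis that may be conducted on safety endpoints". Section 14.3 defines a Safety Population.

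Section 2.1 sets the objective as evaluating both safety and efficacy against Control. Section 2.2 places corneal staining, reported symptoms, slit lamp findings, visual acuity, adverse events and discontinuations ("Number and reasons for discontinuation will be monitored") under its exploratory endpoints. The Synopsis lists the same items as other observations and does not call them exploratory.

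**The concern.** Gating exploratory efficacy claims on the primary and secondary results is a common way to limit over-interpretation. Applied to safety it has no such justification, because a descriptive comparison of staining or symptoms by arm makes no confirmatory claim and needs no protection of the error rate.

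The rule also works in the wrong direction. The worse Test performs on comfort or vision, the more likely the staining and symptom analyses are to be omitted, which is when they could help explain the result. The gate can also close by chance when the two drops are equivalent. Neither event is a reason to leave out a comparison that belongs to the stated objective.

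The exploratory label in Section 2.2 adds a further uncertainty. Section 14.7 specifies no analysis for adverse events, slit lamp findings, visual acuity or discontinuations, so nothing specified for them is lost. The label does, however, leave unclear whether the gate is meant to reach them.

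**Working it through.** **What the gate covers.**

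| Section | Safety content | Gated? | By arm? |
|---|---|---|---|
| 14.7, corneal staining | Tabulation, then further analysis if rates differ | Yes | Yes, stated |
| 14.7, reported symptoms | Relation of symptoms to Test drops if above 5% | Yes | By implication |
| 14.1 | Summary tables of safety variables, as appropriate | No | Not stated |
| 14.3 | Definition of the Safety Population | No | No analysis specified |

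No other part of Section 14 specifies a safety comparison, so both analyses that are (or imply) a between-arm comparison sit behind the gate.

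**How often the gate closes: inputs.** Margin 20 and two-sided 0.05, i.e. one-sided 0.025 (Section 14.2). SD scenarios 25, 30 and 35 (Tables 9 and 10). Historical Control SD 25.74 (Table 8). 52 evaluable per arm (Section 4.1; Table 10 at SD 30). The documents give no SD for the vision VAS, so it is assumed equal to the comfort SD. True comfort deficits of 5 and 10 points are assumptions.

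**Reproducing the plan's sample size.** A noncentral t calculation with true difference 0 and 90% power needs 34, 49 and 66 per arm at SD 25, 30 and 35, as in Table 9. Multiplying by π/3 for the Wilcoxon test gives 35.6, 51.3 and 69.1, rounded up to 36, 52 and 70, as in Table 10. Allowing 10% dropout, 52/0.9 = 57.8, so 58 per arm and 116 in total. The plan's figures reproduce.

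**Formula.** With n = 52 per arm, df = 102 and critical value t = 1.983:

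- SE = SD × √(2/52)
- noncentrality = (20 + Δ)/SE, where Δ is the true Test minus Control difference
- p = P(noncentral t > 1.983)

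Worked case, SD 30 and Δ = 0: SE = 30 × √(2/52) = 5.883; noncentrality = 20/5.883 = 3.40; p = 0.920.

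**No true difference.** The gate needs both hypotheses. With equal SDs, the chance it closes runs from 1 − p (the two tests fully correlated) to 1 − p² (independent).

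| SD | p | Gate closed |
|---|---|---|
| 25 | 0.981 | 0.019 to 0.037 |
| 25.74 | 0.975 | 0.025 to 0.049 |
| 30 | 0.920 | 0.080 to 0.153 |
| 35 | 0.823 | 0.177 to 0.323 |

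**Test truly worse on comfort (assumed).** The chance that the primary alone fails, which is the minimum chance that the gate closes:

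| SD | Δ = −5 | Δ = −10 |
|---|---|---|
| 25 | 0.142 | 0.476 |
| 25.74 | 0.163 | 0.499 |
| 30 | 0.286 | 0.609 |
| 35 | 0.419 | 0.697 |

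These are unadjusted t-test figures. The baseline covariate in Plan A would lower them.

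**The case against.** The strongest reply is that little is really lost. Section 14.1 promises frequency tables for safety variables outside the gate. It does not say by arm for baseline or efficacy variables either, and in a two-arm parallel trial by-arm tables are the natural reading. On that reading the gate removes only the staining comparison and some loosely described follow-up work. The wording about surveillance suggests monitoring during the trial, which cannot wait for a final efficacy result. Case-level review under Sections 11 and 13 continues regardless. Section 14 calls itself a general description, and Section 14.9 refers to a SAP for imputation details; no separate SAP text is among the documents.

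Some of this stands. It would be wrong to say that safety data go unreported if efficacy fails. The symptom item is between-arm only by implication. The closure rates measure how often the gate shuts, not how much safety information is lost. They also depend on assumptions: at 58 per arm, SD 30 and zero difference, the primary fails in 5.5% of trials, not 8%.

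The rest does not remove the problem. By-arm tables under 14.1 have to be inferred, while the gate in 14.7 is explicit, and the plan does not say which prevails. The surveillance wording itself sits under the gate. Review of individual events is not a comparison of arms, and Section 16.4 marks a data monitoring committee as not applicable. The point is confined to Section 14 and does not claim that no other document covers safety.

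**Conclusion.** The concern holds and should be fixed. As written, the only between-arm safety analyses that Section 14 specifies depend on an efficacy result, which conflicts with the comparative safety objective in Section 2.1. The textual finding needs no assumption.

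The size is illustrative. With no true difference the gate closes in 2–4%, 8–15% or 18–32% of trials at SD 25, 30 or 35, and in 2–5% at the historical Control SD. If Test were truly 5 points worse on comfort, the primary alone would close it in 14%, 29% or 42% at SD 25, 30 or 35; if 10 points worse, in 48%, 61% or 70%. All of these assume 52 evaluable per arm and no covariate adjustment. The no-difference ranges also assume a vision SD equal to the comfort SD.

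**What to change.** - In Section 14.7, restrict the gate to exploratory efficacy analyses: the Day-14 comfort and vision VAS and the PRO/MRD items.
- Add one sentence: adverse events, corneal staining, slit lamp findings, visual acuity, reported ocular symptoms and discontinuations will be summarised by treatment arm in the Safety Population whatever the efficacy result.
- In Section 2.2, separate these items from the exploratory endpoints so that the label agrees with the new sentence.

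The cost is wording in two sections plus routine tables on data already being collected. Design, sample size and clinical conduct do not change.

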4. STUDY DESIGN AND RATIONALE

4.1. Description of Study Design

This is a 30-Day multi-site, randomized, single-masked, bilateral, controlled, 2-Arm parallel group, dispensing study. Approximately 116 subjects will be screened and randomly assigned to either Test or Control groups (58 subjects/arm). The goal is for a sample size of 104 (52 subjects/arm) after subjects who withdraw or are lost-to-follow-up. Subjects are scheduled for 3 study visits (screening/baseline, 14-Day, and 30-Day follow-up visits) over a period of one month.

At Visit 1, subjects will be consented and screened for inclusion/exclusion criteria. If a subject is found to meet all eligibility criteria, they will be dispensed with artificial tears eye drops based on the randomization scheme; otherwise, the subject will be discontinued from the study. Subjects will be dispensed with their randomly assigned eye drops and instructed to use them in both eyes, 3-4 times a day, or as needed (not exceeding 6 times a day) over a 14 ± 2 day period. The follow-up evaluation (Visit 2) will occur 14 ± 2 days after Visit 1.

JJVC CONFIDENTIAL

At Visit 2, VAS, PRO and MRD questionnaires, SROS and slit lamp findings will be evaluated, and the subject will be dispensed with a new bottle of drops. Subjects will be instructed to use them in both eyes 3-4 times a day until the next scheduled study visit. Visit 3 will take place 30+/-2 days after Visit 1.

At Visit 3, VAS, PRO and MRD questionnaires, SROS, NITBUT and slit lamp findings will be evaluated, and the subject will have a final evaluation before exiting from the study. All used and unused test articles will be collected from the subjects during the exit visit.

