14.4. Level of Statistical Significance

All planned analysis for this study will be conducted with an overall Type I error rate of 5%. Unless otherwise specified, all statistical tests will be 2-sided.

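### Further analysis of Grade 2+ corneal staining hangs on an unspecified significance test that, at this sample size, would often miss a doubling from a low Control rate

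*Combined protocol and SAP*

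**What the plan says.** Section 2.1 sets the objective as to "evaluate the safety and the efficacy of an Investigational lubricating eye drops (Test) by comparison with Blink" Tears, so safety relative to Control is part of the trial's question.

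Section 14.7 (Other Exploratory Analysis) deals with Grade 2 or higher corneal staining on the FDA scale. Staining "will be monitored by surveillance tabulation by" treatment group. The next step is conditional: "If the rates between groups are significantly different from each other, then further analyses will be performed". The section does not say which test is meant, at which visit, whether the unit is the eye or the subject, or what rate is expected.

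The same section opens with a broader condition: "Exploratory analyses will only be conducted if all primary and secondary hypotheses are met". It assigns these analyses to the Safety population.

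Section 14.4 sets a 5% Type I error rate and says "Unless otherwise specified, all statistical tests will be 2-sided". Section 14.2 bases the sample size on the overall ocular comfort VAS alone. Section 4.1 gives 58 randomised per arm and states: "The goal is for a sample size of 104 (52 subjects/arm) after subjects who withdraw or are lost-to-follow-up".

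**The concern.** For the efficacy endpoints the plan always produces an interval and asks whether it excludes a margin. For staining it asks only whether the arms differ significantly, and specifies nothing further if they do not. In a trial sized for the mean of a 0-100 scale, a non-significant difference in a binary finding is weak evidence of similarity.

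At stake is the comparative safety reading of a signal that the trial does collect. A sizeable excess on Test could appear in the report as two counts, with no difference, no interval and no further analysis. Because no test is named, the same data can also fall on either side of the trigger according to a choice made later.

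**Working it through.** **Inputs from the documents.** 58 subjects per arm randomised and 52 completing (section 4.1); two-sided alpha 0.05 (section 14.4); further analysis only on a significant difference (section 14.7).

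**Inputs not in the documents, assumed here.** The staining rates, the test (Fisher's exact and uncorrected Pearson chi-square are both shown), and the subject as unit.

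**Step 1: the plan's own sample size.** For non-inferiority with margin 20, SD 30, true difference 0, power 90% and one-sided 0.025, the noncentral t calculation gives 49 per arm, as in Table 9. Multiplying by π/3 for the Wilcoxon test gives 49 × 1.047 = 51.3, so 52, as in Table 10. Allowing 10% dropout, 52 / 0.9 = 57.8, so 58 per arm and 116 in total. The stated figure reproduces, and no staining rate enters it.

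**Step 2: power of the trigger.** Power is the sum, over all pairs of counts (i, j) with p ≤ 0.05, of Bin(i; n, p_Control) × Bin(j; n, p_Test). The ranges run from n = 52 to n = 58 per arm.

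| Control v Test (assumed) | Fisher | Chi-square |
|---|---|---|
| 5% v 10% | 7-8% | 15-17% |
| 5% v 15% | 26-31% | 40-45% |
| 10% v 20% | 21-24% | 29-33% |
| 10% v 25% | 43-48% | 53-59% |
| 10% v 30% | 67-72% | 75-80% |
| 15% v 30% | 37-41% | 46-50% |
| 20% v 40% | 52-59% | 62-66% |

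For a doubling, power stays at or below about 50% while the Control rate is 15% or less, and passes 50% at 20%. By the normal approximation, 80% power would need 199 subjects per arm for 10% v 20% and 100 per arm for 10% v 25%.

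**Step 3: one data set, two answers.** Take 14/52 (26.9%) on Test and 6/52 (11.5%) on Control.

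- Difference: 8/52 = +15.4 points.
- Fisher, two-sided: p = 0.080, so no further analysis.
- Chi-square: the pooled rate is 20/104 = 0.1923, and 0.1538² / (0.1923 × 0.8077 × 2/52) = 3.96, p = 0.047, so further analysis.
- Newcombe 95% interval, from Wilson limits of 16.8% to 40.3% (Test) and 5.4% to 23.0% (Control): lower 0.1538 − √(0.1015² + 0.1143²) = +0.1 points; upper 0.1538 + √(0.1333² + 0.0614²) = +30.1 points.

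Against 6/52, Fisher first reaches significance at 15/52 (p = 0.049).

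**The case against.** The strongest reply is that staining is an exploratory endpoint and is not left unwatched. That largely stands:

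- The tabulation by arm in section 14.7 does not depend on the significance test.
- Section 14.1 separately plans summary tables for safety variables.
- Slit lamp findings and staining are assessed at every visit.
- Section 13.1 lists other grade 3 or higher corneal findings as ocular significant adverse events and superficial punctate keratitis as a non-significant one. Section 13.4 sets reporting times for both.

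A reader might infer that a missed excess would trigger nothing at all. The documents do not support that; only the further analysis is withheld. Still, counts carry no measure of uncertainty, and classifying adverse events is not a between-arm comparison of Grade 2+ staining.

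A second reply is that any power figure rests on assumptions outside the plan. That is correct. It would be tempting to say that the test has 21-48% power for a doubling or more, but that range belongs to Fisher's test at 10% v 20-25%. Chi-square gives 29-59% for the same rates, and larger excesses or higher Control rates give more. If eyes were the unit, nominal power would rise: 57% for 10% v 20% with 116 eyes per arm treated as independent, which is an upper bound because fellow eyes are correlated.

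A third reply is that the plan never says a non-significant result shows safety. That is also correct. Such a reading is a risk that the rule invites, not something the text asserts.

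**Conclusion.** The point holds in a limited form. The plan makes every analysis of Grade 2+ staining beyond tabulation depend on a significance test that it does not specify and did not size the trial for. Under assumed rates of 10% v 20-25%, the trigger would fire with about 21-48% (Fisher) or 29-59% (chi-square) probability. For a doubling from 15% or less it would fail about half the time or more under either test. It does not follow that a real excess would usually be missed whatever its size: power exceeds 50% for 20% v 40% and for 10% v 30% under both tests.

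These figures rest on assumed rates, subject-level counts and 52-58 subjects per arm. The criticism of the rule itself does not: 14/52 v 6/52 is flagged by one standard test and not by another. The condition that both non-inferiority hypotheses be met narrows the route further, since the section 14.7 staining analysis may not be run at all if either fails.

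**What to change.** Delete the significance condition in section 14.7 and state instead:

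> For Grade 2 or higher corneal staining, the number and percentage of subjects by arm and the difference (Test minus Control) with a two-sided 95% confidence interval will be reported at each follow-up visit for the Safety population, regardless of statistical significance and of the primary and secondary results; a non-significant difference will not be interpreted as absence of a safety signal.

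This names the unit, visits and population, and frees staining from both conditions in section 14.7. It does not settle how Grade 2 staining already present at baseline is handled. That can occur because section 3.3 excludes only grade 3 or higher, so it would need its own sentence.

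The cost is one sentence and one extra table column from data already collected, with no change to sample size or the primary analysis. The small downside is descriptive intervals without multiplicity control.
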